## 1.4 Analysis Populations

- Intent-to-Treat (ITT)

- **Full Analysis Set (FAS)**

- **Absorb Only Population (AOP)**

## 1.5 Sample Size Calculations

[REDACTED] the sample size of the Surveillance was established as 2000 patients.

The figure consists of a 4x6 grid of black rectangles. The first row contains a single rectangle. The second row contains six rectangles. The third row contains six rectangles. The fourth row contains six rectangles. The rectangles are arranged in a single horizontal row.

## 2. ANALYSIS CONSIDERATIONS

### 2.1 Statistical Methods

Baseline demographic, clinical, angiographic, IVUS/OCT, procedural, and device data, and treatment results will be summarized using descriptive summary statistics.

#### 2.1.1 Descriptive Statistics for Continuous Variables

For continuous variables (e.g., age, percent diameter stenosis and lesion length), results will be summarized with the numbers of observations, means, and standard deviations and where specified in the table mockups, with quartiles, minimums, maximums, and 95% confidence intervals for the means as per the table mockups. Differences between two comparison groups of interest, where specified, will be summarized with relative risks, the differences of the two means, and 95% confidence intervals for the difference between the means. These calculations will be done under the assumption that the data for the two groups of interest are independent and approximately normal in distribution. The confidence interval for the difference of two means will be calculated under the assumption of unequal variances. If the asymptotic assumptions fail, then nonparametric summary statistics (medians, 25th and 75th percentiles) may be displayed as an alternative.

Formulas for calculation of the confidence intervals for the continuous variables are given below:

##### 1. 100(1- $\alpha$ )% Confidence Interval For A Single Mean

$$\bar{x} \pm t_{\frac{\alpha}{2}} \frac{s}{\sqrt{n}}$$

where:

$\bar{x}$  = sample mean

$s$  = sample standard deviation

$n$  = sample size

$t_{\frac{\alpha}{2}}$  = the alpha/2 t - statistic for  $n - 1$  degrees of freedom

##### 2. 100(1- $\alpha$ )% Confidence Interval For The Difference of Two Means Under The Assumption Of Equal Variances Between The Two Groups

$$(\bar{x}_1 - \bar{x}_2) \pm t_{\frac{\alpha}{2}} \sqrt{s_p^2 \left( \frac{1}{n_1} + \frac{1}{n_2} \right)}$$

where:

$\bar{x}_1$  = sample mean for group 1

$\bar{x}_2$  = sample mean for group 2

$$s_p^2 = \frac{(n_1 - 1)s_1^2 + (n_2 - 1)s_2^2}{n_1 + n_2 - 2}$$

$s_1$  = sample standard deviation for group 1

$s_2$  = sample standard deviation for group 2

$n_1$  = sample size for group 1

$n_2$  = sample size for group 2

$t_{\frac{\alpha}{2}}$  = the alpha/2 t - statistic for  $n_1 + n_2 - 2$  degrees of freedom

3. 100(1- $\alpha$ ) % Confidence Interval for the Difference of Two Means under the Assumption of Unequal Variances between the Two Groups

$$(\bar{x}_1 - \bar{x}_2) \pm t_{\frac{\alpha}{2}} SED$$

With the degrees of freedom for the approximate t statistic is determined by Satterthwaite's formula as follows:

$$df = \frac{(w_1 + w_2)^2}{\frac{w_1^2}{n_1 - 1} + \frac{w_2^2}{n_2 - 1}}$$

where:

$\bar{x}_1$  = sample mean for group 1

$\bar{x}_2$  = sample mean for group 2

$s_1$  = sample standard deviation for group 1

$s_2$  = sample standard deviation for group 2

$n_1$  = sample size for group 1

$n_2$  = sample size for group 2

$$SED = \sqrt{\frac{s_1^2}{n_1} + \frac{s_2^2}{n_2}}$$

$$w_1 = \frac{s_1^2}{n_1}$$

$$w_2 = \frac{s_2^2}{n_2}$$

### 2.1.2 Descriptive Statistics for Categorical Variables

For categorical variables such as gender, MACE and TVF, results will be summarized with subject counts and percentages/rates, and where specified in the table mockups, with exact 95% Clopper-Pearson confidence intervals. Differences between the two comparison groups of interest, when specified, will be summarized with the difference in percentages and the Newcombe score 95% confidence interval for the difference of two percentages.

For efficacy and safety endpoint(s), relative risks (i.e., the ratio of rates), confidence interval for the relative risks, the difference in rates and the confidence interval for difference in rates (using previously-described formulas), and p-values may also be presented for hypothesis generating purposes. The p-values will be based on either Pearson's Chi-square test or Fisher's exact test by checking the expected frequency for each cell in the 2x2 contingency table against Cochran's rule, i.e., if the expected frequencies for all cells are  $\geq 5$ , then Pearson's Chi-square test will be used, otherwise Fisher's exact test will be used.

For the determination of event rates at all time points (in-hospital, 3 months and 1, 2, 3, 4 and 5 years), the denominators are defined as below based on the type of events.

- Death/MI/Revascularization (DMR) event

Subjects will be included in the analysis if they either had the DMR event by that time or they did not have the DMR event but had follow-up through that time point. In other words, subjects will be included in a given analysis if it can be determined whether or not the subject would have had the DMR event by the time point.

- Stent/Scaffold Thrombosis (ST)

Subjects will be included in the analysis if they either had the ST by that time or they did not have ST but had follow-up through that time point. In other words, subjects will be included in a given analysis if it can be determined whether or not the subject would have had ST by the time point.

Formulas for calculating confidence intervals for the categorical variables are given below.

1. 100(1- $\alpha$ ) % Exact Clopper-Pearson Confidence Interval for A Single Proportion

$$\text{Lower Confidence Limit} = \frac{x}{x + (n - x + 1)F_{\frac{1-\alpha}{2}}(2(n - x + 1), 2x)}$$

$$\text{Upper Confidence Limit} = \frac{(x+1)F_{\frac{1-\alpha}{2}}(2(x+1), 2(n-x))}{n-x+(x+1)F_{\frac{1-\alpha}{2}}(2(x+1), 2(n-x))}$$

where:

$n$  = sample size

$x$  = number of "events"

$F_{\frac{1-\alpha}{2}}(df_1, df_2)$  = the  $(1 - \alpha/2)$  F - statistic for degrees of freedom  $df_1$  and  $df_2$

2. 100(1- $\alpha$ ) % Newcombe Score Confidence Interval for the Difference of Two Proportions

a. 100(1- $\alpha$ ) % Wilson Score Confidence Interval for A Single Proportion

$$\text{Lower Confidence Limit} = \left( \hat{p} + Z_{\alpha/2}^2 / 2n - Z_{\alpha/2} \sqrt{(\hat{p}(1-\hat{p}) + Z_{\alpha/2}^2 / 4n) / n} \right) / \left( 1 + Z_{\alpha/2}^2 / n \right)$$

$$\text{Upper Confidence Limit} = \left( \hat{p} + Z_{\alpha/2}^2 / 2n + Z_{\alpha/2} \sqrt{(\hat{p}(1-\hat{p}) + Z_{\alpha/2}^2 / 4n) / n} \right) / \left( 1 + Z_{\alpha/2}^2 / n \right)$$

where:

$\hat{p} = x / n$

$n$  = sample size

$x$  = number of "events"

$Z_{\alpha/2}$  = 100(1- $\alpha/2$ )th percentile of the standard normal distribution

b. 100(1- $\alpha$ ) % Newcombe Score Confidence Interval for the Difference of Two Proportions

$$\text{Lower Confidence Limit} = (\hat{p}_1 - \hat{p}_2) - Z_{\alpha/2} \sqrt{L_1(1-L_1)/n_1 + U_2(1-U_2)/n_2}$$

$$\text{Upper Confidence Limit} = (\hat{p}_1 - \hat{p}_2) + Z_{\alpha/2} \sqrt{U_1(1-U_1)/n_1 + L_2(1-L_2)/n_2}$$

where:

$\hat{p}_1$  = sample proportion for group 1       $\hat{p}_2$  = sample proportion for group 2

$L_1$  and  $U_1$  are the lower and upper Wilson Score confidence limits for  $p_1$

$L_2$  and  $U_2$  are the lower and upper Wilson Score confidence limits for  $p_2$

$Z_{\alpha/2}$  = 100(1- $\alpha/2$ )th percentile of the standard normal distribution

### **2.1.3 Survival Analyses**

Survival analysis will be conducted to analyze time-to-event variables. Subjects without events will be censored at their last known event-free time point. Survival curves will be constructed using Kaplan-Meier estimates.

Summary tables for safety and efficacy endpoints will include number of subjects at risk, number of censored subjects, number of events, failure rates (Kaplan-Meier estimates) and standard error of the survival rate for each time interval. For the primary analysis report, all available data will be used.

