##### **1.3.2.1 Clinical Endpoints**

Clinical endpoints will be evaluated in hospital and at each follow-up time point (3 months, and 1, 2, 3, 4, and 5 years).

- Component endpoints
  - Death (Cardiac/Vascular/Non-Cardiovascular)
  - Myocardial Infarction (TV-MI/NTV-MI)
  - Target Lesion Revascularization (ID-TLR/NID-TLR)
  - Target Vessel Revascularization (ID-TVR/NID-TVR)
  - All coronary revascularization
- Composite endpoints
  - DMR (All death/All MI/All revascularization)
  - TVF (Cardiac death/All MI/ID-TVR)
  - MACE (Cardiac death/All MI/ID-TLR)
  - TLF (Cardiac death/TV-MI/ID-TLR)
  - Cardiac death/All MI

Clinical events committee (CEC) will evaluate all deaths and suspected of MIs for 3 years maximally. Surveillance sites will cooperate in providing materials needed to adjudication (e.g., death report, discharged summary) to the Sponsor, if a patient is dead or is suspected to have MI.

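### The Kaplan-Meier failure rates of SAP 2.1.3 censor patients who die without the event, and so modestly overstate 5-year cumulative incidence for endpoints that do not count every death

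*SAP*

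**What the plan says.** SAP 1.3.2.1 sets the horizon: "Clinical endpoints will be evaluated in hospital and at each follow-up time point (3 months, and 1, 2, 3, 4, and 5 years"). Two sets of rates are planned for those time points.

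- **Time-to-event rates (SAP 2.1.3).** "Survival curves will be constructed using Kaplan-Meier estimates", and the summary tables for safety and efficacy endpoints give "failure rates (Kaplan-Meier estimates) and standard error of the survival rate for each time interval". The censoring rule is "Subjects without events will be censored at their last known event-free time point". The section does not mention death and names no competing-risk estimator.
- **Count-based rates (SAP 2.1.2).** "For the determination of event rates at all time points (in-hospital, 3 months and 1, 2, 3, 4 and 5 years), the denominators are defined" for two event types only. For DMR, subjects count if "they either had the DMR event by that time or they did not have the DMR event but had follow-up through that time point". For ST, they count if "they either had the ST by that time or they did not have ST but had follow-up through that time point".

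SAP 1.3.2.1 defines "DMR (All death/All MI/All revascularization"), so any death is a DMR event. TLF, TVF, MACE and cardiac death/MI include cardiac death only. Protocol Attachment 2 classes a death as cardiac unless a non-cardiac cause is unequivocally established.

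The public text of SAP 2.4, Handling of Missing Data, shows only its heading. A rule on death may stand there; nothing below relies on its absence.

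**The concern.** A patient who has died can no longer have an MI or a revascularization. Censoring that patient treats the event as still possible later, at the same rate as in the survivors. The 1-KM figure then describes a population in which nobody dies, and it exceeds the proportion of patients who had the event.

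The stated purpose (Protocol 1, SAP 1.2) is to learn how often adverse events occur in clinical use. That quantity is the cumulative incidence. The gap grows with mortality, hence with follow-up time, and does not shrink with sample size, so it matters most for the 5-year figures.

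Endpoints differ in how much they are exposed:

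- For MI, TLR, TVR and all coronary revascularization, every death without the event competes.
- For cardiac death, cardiac death/MI, MACE, TVF and TLF, only vascular and non-cardiovascular deaths compete.
- For all-cause death and DMR, nothing competes.

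**Working it through.** **Inputs from the documents.** n = 2,000 (SAP 1.5; its derivation is redacted) and T = 5 years. Neither document states a 5-year event rate or mortality rate, so there is no planned figure to reproduce.

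**Assumptions.** Constant hazards and no other loss to follow-up. 5-year all-cause death D = 6%, 10% or 15%. 1-KM values F = 25% (any revascularization), 18% (TVR) and 12% (ID-TLR). For TLF, F = 12% with non-cardiac death of 4%, 7% or 10%.

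**Formulas.** Let H1 = -ln(1-F) and H2 = -ln(1-D) be the cumulative hazards over 5 years.

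- 1-KM with deaths censored = F.
- Cumulative incidence: CIF = H1/(H1+H2) × [1 - (1-F)(1-D)].
- Standard error: SE(KM) = (1-F) × sqrt{ H1/[n(H1+H2)] × [1/((1-F)(1-D)) - 1] }.

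**Worked example, F = 25%, D = 10%.** H1 = 0.2877 and H2 = 0.1054.

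- CIF = 0.2877/0.3930 × (1 - 0.75 × 0.90) = 0.7319 × 0.325 = 23.79%.
- Excess = 25.00 - 23.79 = 1.21 points.
- SE = 0.75 × sqrt(0.7319/2000 × 0.4815) = 1.00 point, so the excess is about 1.2 SE.

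**All cases.**

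| Endpoint (1-KM) | Competing 5-year death | True CIF | Excess, points | Excess / SE |
|---|---|---|---|---|
| Any revascularization (25%) | 6 / 10 / 15% | 24.3 / 23.8 / 23.2% | 0.7 / 1.2 / 1.8 | 0.7 / 1.2 / 1.8 |
| TVR (18%) | 6 / 10 / 15% | 17.5 / 17.1 / 16.7% | 0.5 / 0.9 / 1.3 | 0.6 / 1.0 / 1.5 |
| ID-TLR (12%) | 6 / 10 / 15% | 11.6 / 11.4 / 11.1% | 0.4 / 0.6 / 0.9 | 0.5 / 0.8 / 1.2 |
| TLF (12%) | 4 / 7 / 10% (non-cardiac) | 11.8 / 11.6 / 11.4% | 0.2 / 0.4 / 0.6 | 0.3 / 0.6 / 0.8 |

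**Cross-check from the other direction.** Fix the true incidence at 10%. 1-KM is then 10.15%, 10.25%, 10.53%, 10.82% and 11.13% at competing mortality of 3%, 5%, 10%, 15% and 20%. The relative overstatement runs from about 1.5% to 11% and hardly depends on the event rate. A simulation of 2,000,000 subjects at 10% risk and 10% mortality gave 10.0% with deaths kept in the denominator and 10.5% for 1-KM.

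**Count-based rates of SAP 2.1.2, ID-TLR at 12% and D = 10%.**

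- With the DMR denominator, a patient who died stays in and the rate is the true 11.4%.
- If each component used its own event-free follow-up rule, those patients would drop out. The share alive and event-free is 0.88 × 0.90 = 79.2%, so the rate is 11.4/(11.4 + 79.2) = 12.6%, above the 12% of Kaplan-Meier.

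**ST criteria.** The 3-month rule in Protocol 2.4 is a count (18/2,000 = 0.9%) and does not use Kaplan-Meier. At 2 years, a true ST risk of 1.50% gives 1-KM of 1.51% to 1.55% at 1% to 6% mortality.

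**The case against.** **Censoring at death is inferred.** SAP 2.1.3 speaks of subjects without events and the body of SAP 2.4 is not visible. This stands, and the point has to be worded as an implication of the visible rule. Followed as written, though, that rule gives no other handling.

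**Kaplan-Meier is one of two planned sets.** A reader might infer that all 5-year rates are overstated. The documents do not support that. SAP 2.1.2 also plans counts and percentages at every time point, and with the DMR denominator these keep patients who die. The SAP does not say that this denominator serves the component endpoints, or which set is the reported one.

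**Two estimators are not a contradiction.** A reader might infer that the SAP disagrees with itself, because 2.1.2 may retain a patient whom 2.1.3 censors. That depends on an unstated choice of denominator, and a plan may report both a crude proportion and a Kaplan-Meier estimate. What remains is an ambiguity.

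**Group comparisons use proportions.** A reader might infer that comparisons by sex or diabetes are distorted. The contrasts specified in SAP 2.1.2 are differences in percentages, relative risks and chi-square or Fisher tests; SAP 2.1.3 specifies no between-group Kaplan-Meier contrast.

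**The size is assumed and often small.** This stands. Only any revascularization at 10% death or more and TVR at 15% exceed 1 point; ID-TLR and TLF never do. The TLF cases make about two thirds of deaths non-cardiac (4/6, 7/10, 10/15), which may be too high given the default to cardiac.

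**Conclusion.** The point holds for the Kaplan-Meier rates of SAP 2.1.3, on the reading that deaths without the event are censored. The direction is certain under that reading; the size rests wholly on assumed rates, constant hazards and no other loss. For revascularization endpoints it ranges from about half an SE to just under two. For TLF it stays below one SE, and the other endpoints that count cardiac death are likewise less exposed than the revascularization endpoints.

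The affected endpoints are listed under Other Endpoints and carry no visible threshold, and the ST criteria move negligibly, so no decision rule changes. This is a low-cost improvement in how event frequency is reported. It does not show that the surveillance would reach a wrong conclusion.

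**What to change.** In SAP 2.1.3:

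- State how death is handled. Keep Kaplan-Meier for all-cause death and DMR.
- For endpoints that do not include all-cause death, report the Aalen-Johansen cumulative incidence. The competing event is all-cause death for MI, TLR, TVR and all coronary revascularization. It is vascular and non-cardiovascular death for cardiac death, cardiac death/MI, MACE, TVF and TLF.
- Keep 1-KM as a supportive column for comparison with earlier reports.
- Note that CEC review of deaths lasts at most 3 years (Protocol 7.5, SAP 1.3.2.1), so cause of death in years 4 and 5 is not CEC-adjudicated. This limits the second group of endpoints, not the first.

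In SAP 2.1.2, state that subjects who die stay in the denominator for the component endpoints, and say whether the 2.1.2 or the 2.1.3 rate is the reported 5-year rate.

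The cost is SAP wording and a change of estimation routine. Deaths are already collected, so no new data are needed. The one drawback, weaker comparability with earlier Kaplan-Meier reports, is removed by the supportive column.

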## **2.2 Subgroups for Analysis**

Subgroups, including but not limited to the following, will be evaluated for the FAS and AOP. Baseline demographics, baseline subject characteristics, procedure information, morphology, quantitative coronary angiography, IVUS/OCT, and hierarchical/non-hierarchical adverse event data will be summarized with descriptive statistics. Comparisons will be made within the subgroup when appropriate.

Sex:

- Male
- Female

Diabetes:

- All Diabetes Mellitus
- Non-Diabetes Mellitus

Stent diameter:

- 2.5 mm
- 3.0 mm
- 3.5 mm

## **2.3 Analysis Window**

- Baseline (pre-procedure)
- Procedure
- Post-procedure to discharge
- 3 months (by visit preferred; by telephone is allowed) (Day  $90 \pm 14$  days)
- 1 year (by visit preferred; by telephone is allowed) (Day  $365 \pm 28$  days)

- 2 years (by visit or telephone) (Day  $730 \pm 28$  days)
- 3 years (by visit or telephone) (Day  $1095 \pm 28$  days)
- 4 years (by visit or telephone) (Day  $1460 \pm 28$  days)
- 5 years (by visit or telephone) (Day  $1825 \pm 28$  days)

Scheduled imaging follow-up is not required for this surveillance. If any imaging is performed as site standard practice or is performed for diagnosis, the imaging modality and results should be recorded in case report forms.

#### **2.4 Handling of Missing Data**

#### **2.5 Adjustments for Covariates**

#### **2.6 Multiplicity Issues**

#### **2.7 Documentation and Other Considerations**

All analyses will be performed using SAS® for Windows, version 9.3 or higher.

**3. ACRONYMS AND ABBREVIATIONS**

Acronym/	Description
%DS	Percent Diameter Stenosis
AOP	Absorb Only Population
BVS	Bioresorbable Vascular Scaffold
CEC	Clinical Event Committee
DMR	All Death/All MI/All Revascularization
FAS	Full Analysis Set
ITT	Intent-To-Treat
IVUS	Intravascular Ultrasound
MACE	Major Adverse Cardiac Event
MI	Myocardial Infarction
MLA	Minimal Lumen Area
MLD	Minimum Luminal Diameter
OCT	Optical Coherence Tomography
PMS	Post-marketing surveillance
QCA	Quantitative Coronary Angiography
RVD	Reference Vessel Diameter
SAP	Statistical Analysis Plan
ST	Scaffold/Stent Thrombosis
TIMI	Thrombolysis in Myocardial Infarction
TLR	Target Lesion Revascularization
TVF	Target Vessel Failure
TVR	Target Vessel Revascularization

